**Appendix 3      Criteria for Identifying ECG Measurements of Potential Clinical Relevance**

| Variable   | Criterion Value a                                | Change Relative to Baseline a                              |
|--|---|---|
| Rate  |   |   |
| Tachycardia  | $\geq 120$ bpm  | increase of $\geq 15$ bpm   |
| Bradycardia  | $\leq 50$ bpm   | decrease of $\geq 15$ bpm   |
| Rhythm  |   |   |
| Sinus tachycardia b                       | $\geq 120$ bpm  | increase of $\geq 15$ bpm   |
| Sinus bradycardia c                       | $\leq 50$ bpm   | decrease of $\geq 15$ bpm   |
| Supraventricular premature beat                      | all   | not present $\rightarrow$ present                                     |
| Ventricular premature beat                           | all   | not present $\rightarrow$ present                                     |
| Supraventricular tachycardia                         | all   | not present $\rightarrow$ present                                     |
| Ventricular tachycardia                              | all   | not present $\rightarrow$ present                                     |
| Atrial fibrillation                                  | all   | not present $\rightarrow$ present                                     |
| Atrial flutter                                       | all   | not present $\rightarrow$ present                                     |
| Conduction                                    |   |   |
| 1° atrioventricular block                            | $PR \geq 200$ msec  | increase of $\geq 50$ msec  |
| 2° atrioventricular block                            | all   | not present $\rightarrow$ present                                     |
| 3° atrioventricular block                            | all   | not present $\rightarrow$ present                                     |
| Left bundle-branch block                             | all   | not present $\rightarrow$ present                                     |
| Right bundle-branch block                            | all   | not present $\rightarrow$ present                                     |
| Pre-excitation syndrome                              | all   | not present $\rightarrow$ present                                     |
| Other intraventricular conduction block d | $QRS \geq 120$ msec   | increase of $\geq 20$ msec  |
| Infarction                                    |   |   |
| Acute or subacute                                    | all   | not present $\rightarrow$ present                                     |
| Old  | all   | not present $\rightarrow$ present
$\geq 12$ weeks post-trial entry |
| ST/T Morphological                            |   |   |
| Myocardial Ischemia                                  | all   | not present $\rightarrow$ present                                     |
| Symmetrical T-wave inversion                         | all   | not present $\rightarrow$ present                                     |
| Increase in QTc                                      | $QTcF \geq 450$ msec for males, $\geq 470$ msec for females |   |

aIn order to be identified as potentially clinically relevant, an on-treatment value must meet the “Criterion Value” and also represent a change from the subject’s baseline value of at least the magnitude shown in the “Change Relative to Baseline” column.

bNo current diagnosis of supraventricular tachycardia, ventricular tachycardia, atrial fibrillation, atrial flutter, or other rhythm abnormality.

cNo current diagnosis of atrial fibrillation, atrial flutter, or other rhythm abnormality.

dNo current diagnosis of left bundle branch block or right bundle branch block.

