### **3.7.3.4      *Electrocardiogram Assessments***

Twelve-lead ECG recordings will be obtained after the subject has been supine and at rest for at least 5 minutes. Additional 12-lead ECGs may be obtained per the investigator's discretion and should always be obtained in the event of an early termination. A central ECG service will be utilized for reading all ECGs in order to standardize interpretations for the safety analysis. In addition, ECG results will be evaluated at the investigational site to monitor safety during the trial. The principal investigator or qualified designee will review each ECG reading, noting whether or not any abnormal results are of clinical significance. The ECGs should be repeated 1 time if a result is considered to be clinically significant.

A screening ECG finding of QTcF or QTcN  $\geq 450$  msec for males and  $\geq 470$  msec for females based on the results from the central reader is exclusionary (see [Table 3.4.3.1-1](#) for rollover subjects and [Table 3.4.3.2-1](#) for de novo subjects). In addition, subjects should be excluded if they have any other abnormal ECG finding at screening that, in the investigator's judgment, is medically significant in that it would impact the safety of the subject or the interpretation of the trial results. However, any screening ECG with abnormal result(s) considered to be clinically significant should be repeated as soon as possible to confirm the finding(s) before excluding the subject from the trial. [Appendix 3](#) is provided as a guide for determining potentially clinically relevant ECG abnormalities. For both rollover subjects from Trial 331-10-234 and de novo subjects, central reader results for verification of exclusion criteria at baseline visit will not be available prior to dosing; therefore, subjects will be enrolled based on screening ECG results from the central reader and baseline ECG results from the trial site. However, if the baseline ECG results from the central reader, when available, indicate a QTcF or QTcN  $\geq 450$  msec for males and  $\geq 470$  msec for females at baseline, the investigator must contact the medical monitor to discuss the subject's continued participation in the trial.

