8.2.5 Electrocardiogram Data

A data summary will be provided for the 24-month open-label treatment period only, since there are no ECG measurements in the conversion period.

The ECG measurements will be made at the Week 4 and Month 6, 12, 18, and 24 visits for all enrolled subjects during the 24-month open-label treatment period. The ECG measurements will also be obtained on Day 1 upon entering the open-label treatment period for de novo subjects.

Assessment values and change-from-baseline values in each of the quantitative ECG parameters will be summarized on the OC data by visit and LOCF data for the last assessment visit.

The incidence of clinically significant changes in each ECG parameter will be summarized on the OC data by visit, as well as for the overall open-label treatment period. Refer to Appendix 3 of the protocol for the criteria for identifying ECG measurements of potential clinical relevance. Data of clinically significant changes in ECG parameters will be listed by prior treatment group, subject number, sex, age, body weight, baseline value, visit, description of the findings, and dose at onset of the event.

For the analysis of QT and QTc, data from 3 consecutive complexes (representing 3 consecutive heart beats) will be measured to determine average values. The following QT corrections will be used for reporting purposes in the clinical study report:

- 1) QTcF is the length of the QT interval corrected for heart rate by the Fridericia formula: $QTcF=QT/(RR)^{0.33}$;
- 2) QTcN is the length of the QT interval corrected for heart rate by the Food and Drug Administration (FDA) Neuropharm Division formula: $QTcN=QT/(RR)^{0.37}$.

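### The QTc row that SAP 8.2.5 relies on shows a limit but no change criterion: rises ending below the limit go uncounted and, read literally, a few non-increases can be counted

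*Protocol*

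**What the plan says.** Protocol Appendix 3 lists ECG findings with a criterion value and a change relative to baseline. Footnote a makes both columns binding. Reaching the limit is not enough: a reading has to pass that first test "and also represent a change from the subject’s baseline value of at least the magnitude shown", the size being whatever the second column gives.

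The last row, "Increase in QTc", gives a QTcF limit of 450 msec for males and 470 msec for females. Nothing stands in its change cell. Every other variable has an entry there:

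- rate and sinus rhythm rows: a shift of at least 15 bpm
- PR (limit 200 msec): "increase of $\geq 50$ msec"
- QRS (limit 120 msec): "increase of $\geq 20$ msec"
- remaining rows: a finding that was absent and becomes present

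SAP 8.2.5 states: "The incidence of clinically significant changes in each ECG parameter will be summarized on the OC data by visit". It does the same for the whole open-label period, lists the flagged findings with the baseline value, and refers to Protocol Appendix 3 for the criteria. It adds no criterion for QTc. It also summarizes values and changes from baseline for the quantitative ECG parameters, by visit on observed cases and at the last visit with LOCF. QTcF and QTcN are both to be reported.

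Under Protocol 3.7.3.4, the central reading of the baseline ECG arrives after dosing. If it is at or above the limit, "the investigator must contact the medical monitor to discuss" whether the subject continues.

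**The concern.** The row's name and the SAP's wording both promise a count of changes, but the visible test is of level alone. That can go wrong in two directions. A reading at or above the limit may be counted although the subject has not risen, or has risen by 1 msec. A large rise that stops short of the limit is left out of the incidence table and its listing.

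Safety is this trial's objective, and SAP 8.1 names QT prolongation as a topic of interest. That output rests on adverse event terms and so depends on what investigators report. No planned table counts subjects by the size of their QTc rise.

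**Working it through.** There is no plan figure to reproduce; the check applies the rule to example values. Inputs: limit L = 450 msec (male) or 470 msec (female) from Appendix 3; baseline B; on-treatment value V. As written, with no magnitude in the change cell, the row counts a subject when V ≥ L.

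| Sex | B | V | V − B | Counted as written |
|---|---|---|---|---|
| M | 449 | 450 | +1 | yes |
| M | 455 | 455 | 0 | yes |
| M | 465 | 452 | −13 | yes |
| F | 480 | 471 | −9 | yes |
| M | 380 | 445 | +65 | no |
| F | 400 | 460 | +60 | no |

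**Rises that escape.** The largest whole-msec rise left uncounted is L − 1 − B. Male, B = 380: 450 − 1 − 380 = 69. Male, B = 390: 450 − 1 − 390 = 59. Female, B = 400: 470 − 1 − 400 = 69.

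**When a non-increase can be counted.** V ≥ L and V ≤ B together require B ≥ L. With B below the limit, an unchanged or falling value is never flagged. A baseline at or above the limit is normally exclusionary, but two routes stay open. Under Protocol 3.7.3.4 a late central reading leads to a discussion, not automatic removal. Under exclusion criterion 17 in Table 3.4.3.2-1, a de novo subject with only one of three ECG time points at or above the limit still qualifies.

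**If the cell once held a number d.** The row would then count a subject when V ≥ L and V − B ≥ d. For any d above 0, unchanged and falling values drop out. For any d at all, a rise ending below L stays uncounted, because both conditions are required. The second problem therefore does not depend on the blank cell.

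**Where an uncounted rise can be seen.** SAP 10.6 gives N, mean, SD, median, quartile, minimum and maximum. A +65 msec change is visible as the maximum if it is the largest at that visit. The number of subjects above a given size cannot be read from these statistics.

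**How the documents treat other parameters.** For glucose and lipids, SAP 8.2.1 requires a normal or missing baseline before a value is treatment-emergent, and SAP Appendix 1 has a glucose row based on change alone (any baseline, rise of at least 10 mg/dL). For blood pressure, SAP 8.2.4.1 and Appendix 2 supplement the protocol criteria. Where Protocol Appendix 1 means to ignore baseline, in its orthostatic hypotension row, it says so. The QTc row has none of these.

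**The case against.** The strongest reply has four parts.

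- **A reader might infer that a large individual rise cannot appear anywhere in the output.** The documents do not support that. SAP 8.2.5 with SAP 10.6 reports the maximum change at each visit, so what is missing is a count of subjects.
- **A reader might infer that the table will routinely present stable high values as drug effects.** That is too strong. It needs a normally exclusionary baseline, so few subjects are affected, and the listing prints baseline beside each flagged finding. It also depends on one reading: the label and footnote a could be taken together to mean that a fall never qualifies. The trial is single-arm and descriptive, so no inference rests on the count.
- **The blank cell may be a loss in text extraction.** No redaction is marked and the column's other variable rows survived, but this cannot be excluded.
- **Cut-offs such as 30 or 60 msec do not stand in either document.** Nor do the documents show that flagging on QTcF alone is a mistake. The protocol's nonclinical text reports QT prolongation at 30 mg/kg, but also findings that it takes to suggest low proarrhythmic potential.

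All four stand, and they limit the point. They do not answer the omission of rises below the limit, which holds whether or not a number was lost from the cell.

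**Conclusion.** The point holds in limited form. The only categorical analysis of QTc measurements uses a row whose label, footnote and visible content do not agree. Any rise ending below 450 msec (male) or 470 msec (female) is absent from the incidence table and its listing; in the examples this reaches 69 msec from a baseline of 380 (male) or 400 (female). At the other end, +1 msec is enough to be flagged if it crosses the limit. Flagging of unchanged or lower values is possible but confined to the few subjects with baseline at or above the limit, and it assumes that an empty cell means no change is required. The documents give no QTc distribution, so the number of subjects affected either way cannot be estimated. The example values are illustrations.

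This is a gap in reporting that should be closed before the final database lock. It is not evidence that a QTc effect would be hidden altogether.

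**What to change.** 1. Confirm the change cell against the original Appendix 3 table, and reconcile the row label, footnote a and SAP 8.2.5.
2. In SAP 8.2.5, count the threshold row as treatment-emergent only when baseline is below the limit or the on-treatment value is higher than baseline. Since V ≥ L > B already implies V > B, this reduces to V ≥ L and V > B. It drops 455 to 455 and 465 to 452 (male) and keeps a further rise from a high baseline, such as 455 to 480 (+25). State how a missing baseline is handled, as SAP 8.2.1 does for glucose and lipids.
3. Add a subject-level incidence of increase from baseline in QTcF and QTcN at any post-baseline ECG, in change categories that the sponsor pre-specifies. Categories of 30 and 60 msec are this review's examples, not figures from the documents. Step 2 alone would still leave 380 to 445 uncounted and would still count 449 to 450; this table shows the size of each rise.

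The cost is SAP wording and one additional table on existing central-reader data. No procedure, visit or clinical rule changes.

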## **Appendix 4                    Handling and Shipment of Bioanalytical Samples**

### **Handling of Specimens**

Labels should be secured to each storage tube. Labels should contain the following information: Protocol number; subject number; time point of sample collection (eg, Day 1 predose); and aliquot/matrix (eg, Plasma Aliquot 1 or Plasma Aliquot 2). All tubes must be labeled such that the protocol number, date of collections, and protocol time can be verified. It is important to note the exact time of the blood collection in eSource, not the scheduled time for the drawing.

### **Pharmacokinetic Plasma Samples**

None collected for this trial.

### **Pharmacogenomics Sample**

None collected for this trial.

This page is a manifestation of an electronically captured signature

This statistical analysis plan (SAP) expands the statistical section of Protocol 331-10-236 Amendment 5,¹ and documents in detail the statistical methodologies and data analysis algorithms and the conventions to be applied to the analysis and reporting of safety and tolerability data collected in the trial. All amendments to the protocol have been taken into consideration in developing this SAP.

2 Trial Objectives

The primary objective of this trial is to assess the long-term safety and tolerability of oral brexpiprazole as monotherapy in adolescents (13 to 17 years old) with schizophrenia. Efficacy outcomes such as the Positive and Negative Syndrome Scale (PANSS) ratings over a long-term period will also be assessed, but of secondary interest.

[figure not shown]
3 Trial Design

This is a long-term (24-month), multicenter, single-arm, open-label trial designed to examine the long-term safety and tolerability of brexpiprazole (1 to 4 mg/day) in adolescent subjects, aged 13 to 17 years at the time of informed consent/assent, with a Diagnostic and Statistical Manual of Mental Disorders – Fifth Edition (DSM-5) diagnosis of schizophrenia. Enrollment into the trial will be drawn from eligible subjects who, in the investigator's judgment, could potentially benefit from monotherapy treatment with oral brexpiprazole for schizophrenia and will include rollover subjects from the double-blind, phase 3 efficacy Trial 331-10-234 and de novo subjects from select sites. De novo subjects must have a Kiddie Schedule for Affective Disorders and Schizophrenia - Present and Lifetime version (K-SADS-PL) confirmed DSM-5 diagnosis of schizophrenia. Subjects who roll over from Trial 331-10-234 who turned 18 years old during that trial are also permitted to enroll in Trial 331-10-236. The trial will be conducted on an outpatient basis.

Rollover subjects are restricted to those who are able to rollover within \leq 7 days of the Week 6 visit of Trial 331-10-234. Subjects who are only able to rollover from Trial 331-10-234 after $>$ 7 days from the Week 6 visit may be allowed to enter Trial 331-10-236 as de novo subjects following approval by the medical monitor.

For rollover subjects, Trial 331-10-236 will consist of a 24-month open-label treatment period and a 21-day follow-up period. For de novo subjects, Trial 331-10-236 will consist of a 3- to 28-day screening phase, a 1-to 4-week conversion phase (if applicable), a 24-month open-label treatment phase, and a 21-day follow-up period.

A schematic of the trial design is provided in Figure 3-1 for rollover subjects and in Figure 3-2 for de novo subjects.

AE = adverse event; IMP = investigational medicinal product.

Figure 3-1 Trial Design Schematic - Rollover Subjects from Trial 331-10-234

Screening	Conversion Period ^a	Open-label Treatment Period	Follow-up
Eligible de novo subjects who could potentially benefit from treatment with brexpiprazole for schizophrenia per investigator.	Conversion period only for subjects requiring washout of antipsychotic medications and conversion to brexpiprazole; during 1 to 4 weeks total duration. One or more visits as needed: Day -28 to Day -1	Brexpiprazole dose for de novo subjects who did not participate in the conversion period ^b : 0.5 mg/day on Day 1, increasing to 1 mg/day on Day 5, and have the option to increase in 1 mg increments at subsequent visits, if needed and tolerated, up to a maximum dose of 4 mg; 1 mg decreases permitted at any time to a minimum dose of 1 mg/day for tolerability. ^c Conversion visits: as needed at the end of Weeks 1, 2, and 3	Telephone contact or clinic visit to assess any new or ongoing AEs and to record any concomitant medications Safety follow-up visit 21 (\pm 2) days after last dose of IMP

Conversion Period Baseline **Open-label Treatment Period Baseline (Day 1)** **Up to Month 24**

^aOnly subjects who need to undergo cross-titration to oral brexpiprazole and thus require washout of prohibited medications will participate in the conversion period; baseline assessments for these subjects will be obtained at the baseline (Day 1) visit of the open-label treatment period. Subjects not needing to participate in the conversion period will proceed directly to the baseline (Day 1) visit of the open-label treatment period after completion and review of screening assessments and washout of prohibited medications, provided that all eligibility criteria are met including, but not limited to laboratory test results and ECGs.

^bSubjects who participated in the conversion period will start dosing in the open-label treatment period at the last dose they took in the conversion period.

^cDose adjustments will be made weekly in 1 mg increments to a maximum of 4 mg/day.

^dVisit window of \pm 3 days will be permitted; however, every effort will be made to ensure the individual subject trial participation does not exceed 24 months.

Figure 3-2 **Trial Design Schematic - De Novo Subjects**

4 Sample Size and Power

The sample size for this trial is not based on considerations of statistical power.

Approximately 350 adolescent subjects are anticipated to be enrolled into this 24-month open-label trial with the expectation that at least 100 subjects will have had at least 12 months of exposure to the investigational medicinal product (IMP), brexpiprazole, at the conclusion of the trial.

Enrolled subjects will come from approximately 31 clinical sites across 7 countries.

It is to be noted that following the sample size reduction of the parent Trial 331-10-324 to 315 subjects (Protocol Amendment 3²), less than 350 subjects are expected in Trial 331-10-236.

5 Analysis Populations

To adequately describe the statistical analyses and reporting, three analysis populations are defined as follows.

- Enrolled Sample: consists of all consented/assented subjects who were screened for eligibility and deemed eligible (ie, deemed to have met all the inclusion and none of the exclusion criteria for the current trial).
- Safety Sample: consists of all enrolled subjects who received at least one dose of IMP (brexpiprazole). Subjects will be excluded from this population only if there was documented evidence that the subject did not take any IMP (ie, number of tablets dispensed = number of tablets returned or no IMP dispensed). If a subject was dispensed IMP, but lost to follow-up, the subject will be considered exposed to the IMP.
- Efficacy Sample: consists of all subjects in the Safety Sample who had a baseline assessment and at least one postbaseline assessment of the PANSS Total Score.

Statistical analyses (including summaries) will be performed on the Enrolled Sample for demographics, baseline characteristics, and subject disposition data; on the Safety Sample for adverse events (AEs) and other safety parameters; and on the Efficacy Sample for efficacy parameters.

To facilitate separate analysis and reporting for the 2 sequential periods (ie, the 1- to 4-week conversion period and the 24-month open-label treatment period), 2 subpopulations of the Enrolled Sample and 2 subpopulations of the Safety Sample will be derived as described below.

There are 2 subpopulations of the Enrolled Sample: (1) Enrolled Sample for the open-label treatment period, which consists of (i) rollover subjects; (ii) those de novo subjects directly enrolled into the open-label treatment period; and (iii) those de novo subjects that, as required, underwent a cross-titration conversion period and became eligible for enrollment into the open-label treatment period; and (2) Enrolled Sample for the conversion period, which consists of those de novo subjects that were enrolled in the conversion period, regardless of their eventual eligibility for the subsequent open-label treatment period.

The 2 subpopulations of the Safety Sample are: (1) Safety Sample for the open-label treatment period, and (2) Safety Sample for the conversion period.

6 Trial Conduct

